7.3. Study Monitoring Plan, Auditing, and Inspecting

a. Study Monitoring Plan

The Investigator will allocate adequate time for any monitoring activities deemed appropriate by the Sponsor. The Investigator will also ensure that the monitor or other compliance or quality assurance reviewer is given access to all study-related documents and study-related facilities (e.g., examination rooms, radiology facility, operating room, etc.), and has adequate space to conduct the monitoring visit.

b. Medical Monitoring

It is the responsibility of the Investigator to oversee the safety of the study at his/her site. This safety monitoring will include careful assessment and appropriate reporting of complications as noted in Section 7.2.

c. Auditing and Inspecting

The Investigator will permit study-related monitoring, audits, and inspections by the IRB, the Sponsor, government regulatory bodies, and University compliance and quality assurance groups of all study-related documents (e.g., source documents, regulatory documents, data collection instruments, study data, etc.). The Investigator will ensure the availability for inspections of applicable study-related facilities (e.g., examination rooms, surgical facility, etc.).

In the course of normal study conduct or as revealed in a site monitoring or audit visit, any deviations from the protocol will be documented and as needed corrective action(s) will be initiated.

8. DATA HANDLING AND RECORD KEEPING

8.1. Data Quality Assurance

Data quality is the responsibility of the Investigator. CRF completion may be delegated to other study personnel but the Principal Investigator remains responsible for the accuracy and integrity of all data entered on CRFs. CRFs will be completed and provided to the Sponsor or its designated representative as directed, in an expedited fashion. The Sponsor will work with participating sites to secure data clarification and to obtain additional relevant medical documentation on participants enrolled into this trial.

8.2. Confidentiality

Information about study subjects will be kept confidential and managed according to the requirements of the Health Insurance Portability and Accountability Act of 1996 (HIPAA). Those regulations require a signed subject authorization informing the subject of the following:

- What protected health information (PHI) will be collected from subjects in this study;
- Who will have access to that information and why;
- Who will use or disclose that information;
- The rights of a research subject to revoke authorization for use of one's PHI.

Case report forms will utilize an anonymous subject identifier. The identifier will be composed of the site study ID number, the first letter of the subject's first name, the first letter of the subject's last name, and a sequential subject number by site.

Example: The subject identifier for the fourth-enrolled subject at site 02, whose name is Jane Doe, would be 02-JD-04.

The Investigator is responsible for ensuring that all CRFs and any other documents or media, such as arthroscopic video or still photos, are de-identified prior to sharing with Sponsor.

In the event a subject revokes authorization to collect or use PHI, the Investigator, by regulation, retains the ability to use all information collected prior to the revocation of subject authorization. For subjects who have revoked authorization to collect or use PHI, attempts should be made to obtain permission to collect at least vital status at the end of their scheduled study period.

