5.3. Withdrawal Criteria

Subjects may withdraw from the study at any time prior to the subject’s expected completion and for any reason without prejudice to further treatment. Subjects considered treatment failures will be withdrawn from the study to receive appropriate alternative treatment.

A subject’s participation in the study may be discontinued at any time prior to the subject’s expected completion at the discretion of the Investigator or Sponsor. Reasons for removing a subject from the study include, but are not limited to, the following:

- The subject is uncooperative in adhering to the protocol requirements, including failure to participate in rehabilitation;
- The Investigator believes it is in the best interests of the subject;
- The subject withdraws consent.

The Investigator will attempt to document the subject’s reason for withdrawal on the study completion CRF.

If a subject fails to attend study visits, every attempt shall be made to contact the subject prior to considering the subject lost to follow up and withdrawing the subject from the study.

Subjects who are withdrawn from the study will not be replaced.

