5.1 Primary Endpoint(s)

The primary endpoints include:

- Freedom from reoperation of the index meniscus repair site at 6 months, 1 year, and 2 years;
- Improvements in knee pain and function as measured by KOOS
- IKDC Knee evaluation,
- Lysholm Knee scale, and
- Tegner Activity Scale

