7.4 Derived Data

The study visits for this study are:

Stud Visit 1 = Screening visit

Study Visit 2 = Procedure visit

Study Visit 3 = Day 7-15

Study Visit 4 = Day 90

Study Visit 5 = Day 185

Study Visit 6 = Day 365

Study Visit 7 = Day 730

Analysis Populations

- Indicator for inclusion in the safety population.
- Indicator for inclusion in the analysis population.

Study Duration (will be calculated for each subject):

Study duration [days] = Date of study discontinuation – date of initial surgery

Freedom from reoperation of the index meniscus repair site (will be calculated at each visit):

Proportion of subjects with freedom from reoperation of the index meniscus repair site

$$= \frac{\text{Number of subjects whose known status were without repair}}{\text{Total number of participants with known repair status}} * 100\%$$

Change from pre-operative to post-operative visits in patient reported outcomes:

Change from pre- to post-operative visit will be calculated as:

Post – operative value_{Study Visit n} – Pre – operative value_(Study Visit 1), where n = 4,5,6,

Time since injury:

Time since injury will be calculated as:

Time since injury (in wk) = (Date of surgery – Date of injury)/7

CONFIDENTIAL AND PROPRIETARY

This document contains information that is confidential and proprietary to Smith & Nephew PLC and Smith & Nephew, Inc. and is intended for use only by Smith & Nephew and its manufacturer. It shall not be reproduced or copied in whole or in part, nor shall the contents be disclosed by any means without prior written permission from Smith & Nephew, nor shall anyone make any use of it that is contrary to the expressed or implied wishes of Smith & Nephew

Statistical Analysis Plan	Smith+Nephew
A Prospective, Non-randomized, Multi-Center Investigation of All-suture-based Repair of Horizontal Meniscal Tears (STITCH Study)	Number: CTX-CP001
	Version: 1, 4-Sept-2019
	Page: 10 of 15

Time to re-operation:

Time to reoperation will be calculated as:

Time to re-operation (in wk) = (Date of re-operation surgery – Date of original surgery)/7

Minimal clinically important differences (MCIDs):

- MCID-IKDC (Day185) Indicator = 1 if IKDC difference from baseline to Day 185 > 6.3,
= 0 otherwise;
- MCID-IKDC (Day 365) Indicator = 1 if IKDC difference from baseline to Day 365 > 16.7,
= 0 otherwise;
- MCID-Lysholm (Day365) Indicator = 1 if Lysholm difference from baseline to Day 365 > 10.1,
= 0 otherwise;

Adverse Events

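### The protocol does not require reoperation status to be sought when a subject leaves the study, so the first-listed primary endpoint may be unknown at later landmarks

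*Protocol*

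**What the plan says.** SAP 5.1 lists first among the primary endpoints "Freedom from reoperation of the index meniscus repair site at 6 months, 1 year, and 2 years". The protocol synopsis also aims to characterize a reoperation survival curve, and Protocol 4.1 sets the two-year rate beside historical rates.

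On leaving the study, the documents say this:

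- **Treatment failures** (Protocol 5.3): "Subjects considered treatment failures will be withdrawn from the study to receive appropriate alternative treatment". Protocol 3.2c names meniscectomy as the alternative for these patients and calls it a failure endpoint.
- **Missed visits** (Protocol 5.3): "every attempt shall be made to contact the subject prior to considering the subject lost to follow up and withdrawing the subject from the study".
- **Any withdrawal** (Protocol 5.3): the investigator is to try to record the reason on the study completion form. Withdrawn subjects are not replaced.
- **Revoked authorization** (Protocol 8.2): the investigator "retains the ability to use all information collected prior to the revocation of subject authorization". Beyond that, "attempts should be made to obtain permission to collect at least vital status at the end of their scheduled study period".

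On analysis, SAP 7.4 gives the denominator of the reoperation proportion as "Total number of participants with known repair status". SAP 7.3 uses observed cases. SAP 7.2 limits the Analysis Population to subjects who, among other conditions, did not withdraw early, with an undefined exception for closure. SAP 7.9 gives exact 95% limits and no sensitivity analysis for unknown status.

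**The concern.** This endpoint needs a yes or no and a date, not a clinic visit. It can often be learned after a subject stops attending, yet no section tells the site to ask. The one item named for collection after exit, vital status, is not an efficacy endpoint.

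Exit is also plausibly linked to the outcome. Under 5.3 a failing subject is released to alternative treatment, and under 3.2c that alternative is itself a failure endpoint. Read literally, the plan can release a subject just before the event that it sets out to count, with no instruction to record that event. The SAP then leaves the subject out of the denominator if status is unknown, or out of the Analysis Population for withdrawing early. A different estimator cannot recover an event that nobody recorded.

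**Working it through.** **Inputs from the documents.** Planned N = 30 (Protocol 5.1, SAP 6.1). Three subjects are excluded from all analyses (SAP 6.1), so 30 − 3 = 27. The estimator is known reoperation-free divided by known status (SAP 7.4), with Clopper-Pearson 95% limits (SAP 7.9). Neither document gives a dropout rate, an expected reoperation rate or a sample-size calculation, so there is no stated figure to reproduce. All values of u and r below are assumptions.

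**Formulas.** Let u be the number of unknown status and r the known reoperations.

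- Reported: (N − u − r)/(N − u)
- Worst case, every unknown reoperated: (N − u − r)/N
- Best case, no unknown reoperated: (N − r)/N
- Width of the bounds: u/N, whatever the value of r

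**Per subject.** 1/30 = 3.3 points; 1/27 = 3.7 points.

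**Illustration with N = 30, u = 5, r = 3.** Reported 22/25 = 88.0% (68.8 to 97.5). Worst case 22/30 = 73.3%; best case 27/30 = 90.0%; width 5/30 = 16.7 points. The full-data value could be 88.0 − 73.3 = 14.7 points lower than reported, but only 90.0 − 88.0 = 2.0 points higher. With k reoperations among the five unknown it is (27 − k)/30:

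| k | 0 | 1 | 2 | 3 | 4 | 5 |
|---|---|---|---|---|---|---|
| Full-data value | 90.0% | 86.7% | 83.3% | 80.0% | 76.7% | 73.3% |

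One reoperation among the five is enough to put the full-data value below the reported 88.0%.

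**Illustration with N = 27 and r = 4.**

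| Unknown u | Reported (95% CI) | Bounds | Width |
|---|---|---|---|
| 0 | 23/27 = 85.2% (66.3 to 95.8) | none | 0 |
| 2 | 21/25 = 84.0% (63.9 to 95.5) | 77.8 to 85.2% | 7.4 |
| 3 | 20/24 = 83.3% (62.6 to 95.3) | 74.1 to 85.2% | 11.1 |
| 5 | 18/22 = 81.8% (59.7 to 94.8) | 66.7 to 85.2% | 18.5 |
| 8 | 15/19 = 78.9% (54.4 to 93.9) | 55.6 to 85.2% | 29.6 |

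**The early-withdrawal rule.** SAP 7.2 ties only the Analysis Population to the primary variable, as supportive evidence. It does not say whether a subject withdrawn as a failure has withdrawn early. If so, an assumed 4 failures among 27 would turn 23/27 = 85.2% (66.3 to 95.8) into 23/23 = 100% (85.2 to 100). This shows why the rule needs stating; it does not predict what the sponsor will do.

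**The case against.** Several stronger readings are tempting, and the documents do not support them.

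- **That vital status is all that may be collected.** Protocol 8.2 says at least vital status, which is a floor, and the sentence covers only subjects who revoke authorization. For everyone else the gap is the silence of 5.3.
- **That status is unknown for every dropout.** A subject withdrawn because of a reoperation has a known event. One who leaves after day 185 or day 365 has known status at the landmarks already passed. Data collected before revocation stay usable.
- **That nothing could capture a later event.** Protocol 5.3 requires contact attempts before a subject is declared lost. Protocol 7.2 has complications followed until they resolve, stabilize or are found not to be caused by the repair. Protocol 8.1 lets the sponsor obtain further medical documentation. A reoperation form (CRF-008) exists. The forms themselves and the consent pages are not available here and may already ask. These routes make the fix feasible, but none is tied to reoperation status after exit.
- **That a call or chart check would always settle it.** Lost subjects may be unreachable, a site chart may miss surgery elsewhere, and revocation requires new permission.
- **That the reported rate is shown to err favourably.** It is not. If no unknown subject was reoperated, the reported figure is too low (81.8% against 85.2% in the N = 27 case with five unknown). Favourable bias is plausible because failures are released, but it remains an inference.

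It can also be said that the bounds of 73.3 to 90.0% fall inside the exact interval of 68.8 to 97.5%. That is true, but the interval reflects sampling error in the known subjects only. The worst case of 22/30 has its own exact interval, 54.1 to 87.7%, which reaches well below 68.8%.

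Finally, this is a small single-arm study with no formal hypothesis or sample-size calculation. That fairly lowers the severity. It does not remove the point, because describing the reoperation rate is a main purpose of the study.

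**Conclusion.** The point holds in this form: neither document requires reoperation status to be sought when a subject withdraws, is discontinued, is withdrawn as a failure or is lost. Status at landmarks not yet reached may then be unknown, possibly for reasons related to the outcome. The SAP handles this with a known-status denominator and an early-withdrawal exclusion, without a sensitivity analysis.

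The firm part of the size is 3.3 points (N = 30) or 3.7 points (N = 27) per unknown status. Totals depend on a dropout count that the documents do not give; the 16.7-point range for five unknown of 30 is an illustration. The conclusion rests on the text of the protocol and SAP, and would soften if the case report forms already ask for reoperation status at exit. It should be fixed, but it does not invalidate the study.

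**What to change.** **Protocol 5.3.** Add a sentence: for every subject who leaves early, for whatever reason, any reoperation on the study meniscus (yes/no, date, type) is recorded at exit and sought again at the 2-year date by telephone or chart review, on CRF-008 and CRF-009. This concerns data collection only and leaves the rules on withdrawing or treating failures untouched.

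**Protocol 8.2.** Extend the minimum sought after revocation from vital status to vital status and reoperation status, with the subject's permission.

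**SAP 7.2 and 7.4.**

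- Do not exclude subjects from the reoperation endpoint for early withdrawal.
- Count subjects withdrawn because of reoperation as events.
- Set status at 6 months, 1 year and 2 years from the reoperation date, which SAP 7.4 already uses for time to reoperation.
- Report worst-case and best-case bounds for statuses still unknown.

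**Cost.** One question at exit and one call or chart check per leaver, plus IRB approval and any permission needed. SAP 6.1 says that accrual is complete, so for subjects already gone the check is retrospective. Some statuses will stay unknown, which is why the bounds are needed even after the change.

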8.3. Source Documents

Source data is all information, original records of clinical findings, observations, or other activities in a clinical trial necessary for the reconstruction and evaluation of the trial. Source data are contained in source documents. Examples of these original documents, and data records include: hospital records, clinical and office charts, laboratory notes, memoranda, physician-completed study forms, recorded data from automated instruments, copies or transcriptions certified after verification as being accurate and complete, microfiches, photographic negatives, microfilm or magnetic media, x-rays, subject files, and records kept at the pharmacy, at the laboratories, and at medico-technical departments involved in the clinical trial.

8.4. Case Report Forms (see Appendix 6)

The study case report form (CRF) is the primary data collection instrument for the study. All data requested on the CRF must be recorded. All missing data must be explained. If a space on the CRF is left blank because the procedure was not done or the question was not asked, "N/D" will be entered. If the item is not applicable to the individual case, "N/A" will be entered. All entries should be printed legibly in black ink. If any entry error has been made, to correct such an error, a single straight line will be drawn through the incorrect entry and the correct data will be entered above it. All such changes must be initialed and dated. Errors will not be erased or obliterated (i.e. use of Wite-out). For clarification of illegible or uncertain entries, clarification may be printed above the item, initialed and dated.

8.5. Retention of Trial Documents and Records

Trial documents and records are to be retained at least until 2 years following the official end of the study at all sites.

9. STATISTICAL PLAN

9.1. Subject Population(s) for Analysis

Data obtained from all enrolled subjects will be analyzed on a per-treatment (PT) basis, which will include all enrolled subjects who receive the protocol-defined treatment of suture-based meniscal repair.

9.2. Statistical Methods

Appropriate descriptive statistics will be presented for baseline characteristics, procedural variables, reoperation rate of the index meniscal repair site, and major complications. Logistic regression will be fitted to determine baseline predictors of various outcome measures. Independent variables for these models will include but may not be limited to, tear compartment, circumferential length of tear, primarily horizontal vs. oblique, subject age, subject gender, subject BMI, study site, partial meniscectomy vs. no meniscectomy, meniscal surgical technique.

Justification for data pooling will be made on a clinical basis.⁴⁸ These criteria call for use of the same protocol requirements at all sites, the sponsor to monitor the sites for compliance with the protocol, and the use of similar data collection procedures at all sites. Since this study does not include a control group, no analysis of the interaction of the treatment effect with clinical site is possible. Reoperation rates will be evaluated by clinical center.

Subject and reported outcome measures, KOOS, IKCD Knee Evaluation, Lysholm Knee Questionnaire and Tegner Activity Scale outcome assessments will be summarized and thoroughly characterized across time with the appropriate descriptive statistics including error measures. Statistics may include mean, mode, median, range, inter-quartile range, minimum, maximum and frequency, cumulative frequency percentage and cumulative percentage. Results will be presented in narrative and graphically.

These measures will also be analyzed using inferential statistics. As appropriate a repeated measure ANOVA or Wilcoxon signed rank test will be completed for each outcome measure. If a significant trend is identified, significance among time points, especially preoperative measures, may be further explored using the appropriate pair-wise comparisons. In all cases a p value equal to or less than 0.05 will be considered significant.

10. ETHICAL CONSIDERATIONS

10.1. IRB Review

This protocol and any amendments will be submitted to a properly constituted Institutional Review Board (IRB), in agreement with local legal prescriptions, for formal approval of the study conduct. The decision of the IRB concerning the conduct of the study will be made in writing to the Investigator and a copy of this decision will be provided to the Sponsor before commencement of this study. The Investigator should provide a list of IRB members and their affiliate to the Sponsor.

10.2. Informed Consent

All subjects for this study will be provided a Subject Informed Consent Form describing this study and providing sufficient information for subjects to make an informed decision about their participation in this study. This consent form will be submitted with the protocol for review and approval by the IRB for the study. The formal consent of a subject, using the IRB-approved consent form, must be obtained before that subject undergoes any study procedure. The subject must sign and date the consent form. No surrogate for the subject may sign on the subject's behalf.

11. CONFLICT OF INTEREST

Investigators who have a conflict of interest with this study (e.g., patent ownership, royalties, or financial gain greater than the minimum allowable by their institution,

etc.) must have the conflict reviewed by a properly constituted Conflict of Interest Committee with a Committee-sanctioned conflict management plan that has been reviewed and approved by the Sponsor prior to participation in this study.

12. PUBLICATION PLAN

Sponsor-selected Principal Investigators will facilitate the publication of the results (in part or in whole) of the study. Neither the complete nor any part of the results of the study carried out under this protocol, nor any of the information provided by the Sponsor for the purposes of performing the study, will be published or passed on to any third party without the consent of the Sponsor. Any Investigator involved with this study is obligated to provide the Sponsor with complete test results and all data derived from the study. Interim study results may be presented or published after each study interval.

14. STUDY ACTIVITY SCHEDULE

STUDY ACTIVITY SCHEDULE

Activity	Visit 1	Visit 2	Visit 3	Visit 4	Visit 5	Visit 6	Visit 7
	Screen < 4 weeks	Procedure	7-15 Days	90 Day ±7 days	185 Day ±14 days	365 Day ±30 days	730 Day ±30 days
Informed consent	X						
Screening Inclusion / Exclusion	X						
Demographics / Medical History	X						
Radiographs	X ^{1,5}						X ¹
MRI	X ⁵					X ²	
Images		X ³					
Arthroscopy Inclusion / Exclusion		X					
Study Procedure		X					
Details of Procedure		X					
Details of Pathology		X					
Safety Follow-Up			X	X	X	X	X
KOOS	X			X	X	X	X
IKDC Subjective	X			X	X	X	X
Lyshlom	X			X	X	X	X
Tenger	X			X	X	X	X
In-office Arthroscopy					X⁴		

¹Standing AP X-ray

²MRI 1.5 T or greater, no contrast to be reviewed by independent radiologist appointed by sponsor.

³Video, still photographs and diagrams of procedure.

⁴If available.

⁵ Within 6 months of Procedure

15. LIST OF ATTACHMENTS

Appendix 1	ISAKOS Criteria
Appendix 2	Cartilage Guidance
Appendix 3	Modified Outerbridge Scale
Appendix 4	Kellgren-Lawrence Grading Scale
Appendix 5	Subject Informed Consent Form
Appendix 6	Case Report Forms
	
• 001 Screening Inclusion Exclusion• 002 Demographics and History• 003 Arthroscopy Inclusion Exclusion• 004 Details of Pathology• 005 Details of Procedure• 006 Safety Follow-Up• 007 Complication• 008 Details of Reoperation• 009 Study Completion• 010 Protocol Deviation• 011 Data Clarification• 012 KOOS• 013 IKDC Subjective Knee Evaluation• 014 Lysholm Knee Questionnaire• 015 Tegner Activity Scale• 016 Meniscus Repair Assessment
Appendix 7	Imaging Guidance
